## **XII. Data Management Plan**

Study coordinators will securely manage all data and PHI in accordance with HIPAA and IRB regulations, and maintain data confidentiality and anonymity. The only physical study document that will contain identifiable information will be the informed consent document, which the study coordinator will store in a secure, locked location until it can be securely transferred to a locked cabinet at the University of Alabama at Birmingham (UAB). All other study documents will only contain the patient's UID, but no identifiers.

The CSC and BSC will transmit all study documents to [name], the study statistician, for data analysis. This includes questionnaires, fidelity checklists, data collection sheets, spreadsheets, and any other data collection instruments and tools.

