## **VII. Randomization Plan**

The randomization scheme will be executed via REDCap, a clinical trials management software program. Participants will be randomly assigned to group (1:1) using a computer-generated program overseen by [name]. The randomization scheme will be stratified by site (SC, AL, MS) race (W, AA), and illness trajectory. As the Central Coordinating Site, UAB will manage the randomization process. The UAB study manager will be alerted to the assignment by REDCap and will trigger the local unblinded study coordinator to communicate assignment to the participant and initiate study protocol. All other members of the research team will remain blind to group assignment and participants will be instructed not to discuss their assignment with the local study coordinator collecting the outcome assessments.

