**b. Fidelity checklist**

The CSC will fill out the fidelity checklist for each PC consult, to track the PC physician's adherence to the cultural guidelines. The fidelity checklist will contain the patient UID, the date, and the duration of the PC consult.

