**c. Data collection sheet**

The CSC will fill out a data collection sheet for each patient (both Group A and Group B), using patient's UID. The data collection sheet will record:

- Demographics
- Diagnosis
- Readmissions
- Study group
- PC recommendations
- Family implementation of PC recommendations (determined via family interview)

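### Section VII keeps everyone but the study manager and the unblinded local coordinator blind, yet Section XII sends the statistician files that reveal each patient's arm

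*Combined protocol and SAP*

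**What the plan says.** Section VII describes who learns the assignment: "The UAB study manager will be alerted to the assignment by REDCap and will trigger the local unblinded study coordinator to communicate assignment". It then states: "All other members of the research team will remain blind to group assignment". The statistician is not named as an exception.

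The opening of Section XII has both site coordinators (CSC and BSC) send all study documents to a person described as "the study statistician, for data analysis", and spells out the contents: "This includes questionnaires, fidelity checklists, data collection sheets, spreadsheets, and any other data collection instruments and tools". It gives no date, masking step or database lock.

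The later parts of Section XII describe those files:

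- **Fidelity checklist (XII.b).** "The CSC will fill out the fidelity checklist for each PC consult", and "The fidelity checklist will contain the patient UID, the date, and the duration of the PC consult".
- **Data collection sheet (XII.c).** "The CSC will fill out a data collection sheet for each patient (both Group A and Group B), using patient's UID". Its listed fields include study group, PC recommendations and the family's implementation of them, alongside diagnosis and readmissions.
- **Implementation spreadsheet (XII.a).** It tracks each consult by UID and lists the recommendations made.

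Section IV gives the consult to one arm only, 176 of 352 patients. Section XI puts into the regression models whichever demographic and stratification variables turn out to differ between arms, with race entered separately. It gives no significance level or size of difference that counts as differing.

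**The concern.** The two sections cannot both be followed as written. If the statistician is among those kept blind, Section XII breaks that blind for every patient. If the statistician is not, Section VII is wrong about who is blind.

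The practical stake lies in Section XI. The covariate set is unsettled until someone compares the arms, and the person doing so would hold true arm and Day 7 ESAS for the same UIDs. Nothing in the plan requires the model to be settled before those files are received. A reader who relies on Section VII would credit the analysis with a protection that the data flow does not provide.

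**Working it through.** The plan attaches no figure to this point, so the check is mainly a comparison of sections.

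**Step 1. What each transmitted file reveals.**

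| File (Section XII) | Exists for | Linked by UID | Reveals arm through |
|---|---|---|---|
| Data collection sheet | every patient, both arms | yes | study-group field; recommendation fields |
| Fidelity checklist | each consult | yes | its existence |
| Implementation spreadsheet | each consult | yes | presence of an entry |
| Questionnaires | every patient, both arms | yes | nothing alone, but they link to the rows above |

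**Step 2. Coverage.** The arms are 176 + 176 = 352. The study-group field covers all 352. The checklists cover at most 176. A missing checklist does not prove usual care, since a consult may not have taken place, so the study-group field is what makes identification complete.

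**Step 3. Would a letter code hide the arm?** No. Even if Group A and Group B are masked labels, checklists and recommendations arise in one arm only and show which letter is the intervention.

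**Step 4. How open is the covariate rule?** The Measures table (Section X) gives 10 demographic items. Assume k = 10 independent candidates (range 9 to 12) and a threshold a for calling a variable different. The chance that at least one differs by luck is 1 − (1 − a)^k:

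- a = 0.05: 1 − 0.95^10 = 40% (37% to 46% for k = 9 to 12)
- a = 0.10: 1 − 0.90^10 = 65% (61% to 72%)
- a = 0.20: 1 − 0.80^10 = 89% (87% to 93%)

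The unstated threshold therefore matters to which model is fitted.

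**Step 5. What an open set could cost.** This is an illustration on assumed inputs: 4,000 simulated null trials, n = 352, 10 independent normal covariates jointly explaining 0%, 10% or 30% of outcome variance. Two-sided type I error at a nominal 0.05:

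| Variance explained | All 10 covariates, fixed | Rule fixed in advance at p < 0.05 | Smallest p of five sets |
|---|---|---|---|
| 0% | 0.050 | 0.050 | 0.059 |
| 10% | 0.052 | 0.052 | 0.069 |
| 30% | 0.054 | 0.045 | 0.089 |

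The five sets are none, p < 0.05, p < 0.10, p < 0.20 and all. Simulation error near 0.05 is about √(0.05 × 0.95 / 4000) = 0.003.

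A two-sided p-value is unchanged when the arm labels are swapped. The last column therefore measures the effect of an open covariate set, and it would arise under a masked code too. It does not measure loss of masking.

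**The case against.** The strongest reply is that the Section VII sentence cannot be literal. The remote physician and interdisciplinary team deliver the consult, so they know the arm. The same sentence goes on to protect the coordinator who collects outcomes, and Section X names the T2/T3 coordinators as the blinded staff. On this reading the real safeguard is assessor blinding, which the Section XII data flow does not break. That stands as far as it goes: nothing here shows that outcome assessment is unblinded. But the sentence is written without exceptions, and no other passage exempts the statistician.

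The name of the person overseeing randomization has been removed, so it cannot be told whether that is the statistician. If it is, Section VII needs an explicit exception.

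It is also fair that a statistician must eventually use group labels, and that the open rule in Section XI, more than loss of masking, is the main route to bias. Both are accepted. A masked code alone would not cure the problem. The regression models that Section XI announces do not appear in the text available, so a threshold stated there cannot be excluded.

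Three stronger readings are tempting and are not supported:

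- A reader might infer that the statistician watches arms and outcomes accumulate during recruitment. Section XII gives no transfer date, so this is possible but not stated.
- A reader might infer that the trial promises a blinded analysis that would be untrue. The documents plan no such report.
- A reader might take 0.059 to 0.089 as the harm from unblinding. Step 5 shows why it is not.

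**Conclusion.** The contradiction is real. As written, Section XII gives the statistician the arm of every patient, up to all 352, while Section VII says the rest of the team stays blind. The stated blind does not hold for the statistician.

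The size of any bias cannot be derived from the documents. It depends on when the files are sent and on how many covariate choices are made after outcomes can be seen by arm. The simulation shows only that an open set can matter, under its assumed inputs.

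The conclusion rests on the statistician counting as a member of the research team under Section VII and on no exception existing in removed text. It deserves correction because the remedy is cheap and the Section XI rule leaves room for choice. It does not call into question the blinding of the outcome assessors.

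**What to change.** 1. **Section XII, routing.** Send the fidelity checklists, the implementation spreadsheet, and the study-group and PC-recommendation fields of the data collection sheet (including family implementation) to the UAB study manager, who already knows the assignment. Release them for the fidelity and mediator analyses only after the model is signed off and the database locked.
2. **Section XII, what the statistician receives until then.** Questionnaires, diagnosis, readmissions and other resource-use data, stratification factors and a masked A/B code. Readmissions must be carried over explicitly, because they are a secondary outcome recorded on the same sheet as study group.
3. **Section XI.** Replace selection by observed difference with a fixed covariate list, for example site, race, illness trajectory and baseline ESAS, settled before any outcome data by arm are seen. This is needed because masking alone does not prevent choice among covariate sets.
4. **Section VII.** List who is unblinded (study manager, CSC, remote physician and interdisciplinary team, local clinicians) and state the statistician's status. If the statistician is to be unblinded, say so; item 3 is then the essential protection.

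Cost: the study manager must split and mask the site files, which include coordinator-kept spreadsheets and sheets, so this is more than an export setting. The fidelity and mediator analyses start later. Sample size and patient procedures do not change.

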### **a. Spreadsheets**

Each CSC and BSC will maintain a number of spreadsheets and documents to track all aspects of data collection at their respective sites.

#### **Referral spreadsheet**

One spreadsheet should track potential patient referrals. No identifiable information should be included in the spreadsheet. The spreadsheet should include the following:

- Referral number (e.g., 'referral 001')
- Date of referral
- Name and title of person making referral (e.g., 'Nora, nurse')
- Patient age, ethnicity, sex
- Patient diagnosis
- Name of treating clinician
- Whether or not treating clinician's permission was granted
  - If no, why not?
  - Date of treating clinician's permission/denial
- Whether or not patient enrolled'
  - If no, why not?
  - Date of patient's enrollment/non-enrollment
  - If yes, patient UID

**UID spreadsheet/linkage log.** The linkage log will be the only spreadsheet that contains PHI/identifiable patient information. It will contain the patient's UID, patient's name, caregiver's name, and phone numbers. This spreadsheet should be password encrypted, and shared only with members of the study team.

**Implementation of PC recommendations spreadsheet.** The PC recommendations and implementation spreadsheet will track each patient consult using the patient UID. It will contain a list of each of the PC recommendations, and whether or not each of the recommendations was implemented by the treating clinician(s).

**b. Fidelity checklist**

The CSC will fill out the fidelity checklist for each PC consult, to track the PC physician's adherence to the cultural guidelines. The fidelity checklist will contain the patient UID, the date, and the duration of the PC consult.

**c. Data collection sheet**

The CSC will fill out a data collection sheet for each patient (both Group A and Group B), using patient's UID. The data collection sheet will record:

- Demographics
- Diagnosis
- Readmissions
- Study group
- PC recommendations
- Family implementation of PC recommendations (determined via family interview)

**d. Questionnaires**

The DSC will send completed questionnaires (either hard copies or electronic copies) to [name] for analysis. Each questionnaire will only have the patient UID, and no identifiable information.

### **XIII. Confidentiality/Privacy Considerations**

Information obtained about the patient/caregiver will be kept confidential to the extent allowed by law. However, research information that identifies the patient/caregiver may be shared with people or organizations for quality assurance or data analysis, or with those responsible for ensuring compliance with laws and regulations related to research. They include:

- The UAB Institutional Review Board (IRB). An IRB is a group that reviews the study to protect the rights and welfare of research participants.
- National Institute of Nursing Research/NIH/DHHS
- The Office for Human Research Protections (OHRP)

The information from the research may be published for scientific purposes; however, the patient/caregiver's identity will not be given out. All study documents and data sent electronically via HIPAA compliant system will be stored in a secure, locked file cabinet at the University of Alabama at Birmingham (UAB).

#### **XIV. Study Risks and Discomforts**

This study has very low risk to participants. Risks that they potentially incur include:

- a. **Emotional distress:** Talking about their illness and symptoms may cause emotional distress for patients or caregivers. Patient may get tired while answering the questions with the study coordinator. If a patient gets too tired, we can come back later in the day. Sometimes people feel embarrassed or uncomfortable when being asked questions so patients/caregivers can refuse to answer any question.
- b. **Loss of confidentiality:** There is a chance that people not associated with the study will see patient/caregiver answers to questionnaires. Patient/caregiver name and other identifying information will be removed from study documents. Data will be kept in locked files in the study research offices at UAB. All data will be housed in a secure, password protected database at UAB.
- c. **Burden and benefits:** There is a risk related to being placed into a group by chance (i.e., randomization). Patients in the standard care group may not have the same benefits as patients in the intervention group.

#### **XV. Patient/Caregiver Payment for Participation in Research**

The patient and the caregiver will be paid \$10 for completion of baseline questionnaires, \$10 for completion of Day 7 questionnaires, and \$20 for completion of the Day 30 questionnaire. The total payment you may receive is \$40. If the patient/caregiver does not finish the entire study, they will be paid at the time they decide to stop taking part in the study.
